### 3.1 General Design

**Study Schema:** Eligible subjects will receive highly engineered plasmid DNA encoding HPV-16 and HPV-18-E6 & E7 transcription unit antigens (VGX-3100) combined with the DNA encoding IL-12 (INO-9012) followed by EP with the CELLECTRA®5P device.

**COHORT I:** Immunotherapy will be given both before and after definitive surgery. Each subject will receive a total of 4 doses of treatment, 1-2 of them pre-surgery. Each treatment will be 6 mg

of VGX-3100 and 1 mg INO-9012 (INO-3112) delivered IM followed by EP. A minimum of 5 eligible subjects will be enrolled to this cohort.

**Pre-Surgery:**

- 1) Subjects will be enrolled if they have confirmed HPV positive mucosal HNSCCa. Tumor tissue samples must be available to perform immunological correlates prior to definitive surgery.
- 2) After providing informed consent and being deemed eligible, subjects will receive immunotherapy. Up to 2 doses may be administered approximately once every 3 weeks ( $\pm 3$  days) prior to definitive surgery.
- 3) The number of pre-surgery immunotherapies (one vs. two injections) will be based on the estimated time interval between pre-surgery evaluation and definitive surgery. Time to surgery according to standard practice is usually 2- 4 weeks; however, this varies due to ordinary logistical considerations independent of a clinical trial.
- 4) Surgery will not be delayed to allow for immunotherapy.

**Post-Surgery:**

- 1) Subjects will be seen approximately 2 weeks ( $\pm 7$  days) post-surgery for follow up.
- 2) Subjects will undergo visual inspection to document healing by surgeon approximately 4 weeks post-surgery.
- 3) Post-surgery immunotherapy will proceed only after approval of the surgeon.
- 4) Subjects will receive up to 3 doses given 3 weeks ( $\pm 3$  days) apart. A total of 4 doses (pre- and post-surgery) will be administered.
- 5) Immunotherapy will be administered prior to adjuvant chemotherapy and/or radiation that may be indicated.
- 6) Adjuvant therapy will not be delayed for immunotherapy.
- 7) Subjects will be followed for tumor status as per institutional standard of care.

**COHORT II:** Immunotherapy will start approximately 2-6 months after completion of definitive or adjuvant chemoradiation therapy in order to allow recovery from the treatment side effects of chemoradiation. INO-3112 (6 mg of VGX-3100 and 1 mg INO-9012) will be delivered by IM injection with EP once every 3 weeks ( $\pm 3$  days) for a total of 4 doses. A minimum of 10 subjects will be enrolled into this cohort.

- 1) Subjects will be enrolled if they have HPV-16 and/or HPV-18 positive HNSCCa confirmed by ISH or PCR, and have completed chemoradiation therapy. Adequate tissue must be available to perform immunological correlates studies. Confirmation of HPV-16 and/or HPV-18 positivity is required prior to first dose of immunotherapy.
- 2) Subjects will be followed for tumor status as per normal institutional standard of care.

**Sample Size:** A minimal of 20 but no more than 25 eligible subjects will be enrolled in this study.

## 3.2 Study Endpoints

### 3.2.1 Primary Endpoint

The primary study endpoint is safety and tolerability based on standard laboratory and clinical adverse event monitoring:

1. Adverse events will be measured and graded according to “Common Terminology Criteria for Adverse Events (CTCAE)”, NCI version 4.03 issued by the US Department of Health and Human Services.
2. Frequency and severity of injection site reactions including administration site pain, skin erythema, induration, bleeding, tenderness and infection.

### 3.2.2 Secondary Endpoint

The secondary endpoints is immune response after immunotherapy based on correlative measures:

1. Measure HPV-16 and HPV-18 specific antibody levels. A standardized binding ELISA will be performed to measure the anti-HPV16/18 E6 or E7 antibody response induced by VGX-3100 and INO-9012. 96-well enzyme immunoassay plates will be coated with HPV16 or HPV18 E6 or E7 proteins (1 µg/ml) (recombinant HPV16/18 E7 and HPV16 E6 procured from ProteinX Lab, HPV18 E6 from Impact Biologicals). Subject sera will be diluted with 1% bovine serum albumin in PBS and tested in triplicate with an automated and calibrated plate washer and read on a kinetic microplate reader (Molecular Devices). Samples will be scored as positive if the average optical density (OD) was greater than 0.15 absorbance units and greater than the average OD before preimmunization plus 2.5 times the standard deviation of the OD compared to corresponding preimmunized samples at the same dilution.
2. Using Antigen-specific IFN-γ ELISpot assays, determine the number of antigen-specific spot forming units (SFU) in response to stimulation with HPV16 and HPV18. T cell responses will be assessed using an HPV IFN-γ ELISpot assay. PBMCs will be thawed and plated at 200,000 cells/well. Cells will be incubated with HPV16 and HPV18 peptides corresponding to E6 and E7 proteins of HPV. The three sets of peptides, each contain 15–amino acid residues overlapping by 8 amino acids representing the entire consensus E6/E7 fusion protein sequence of HPV16 or HPV18, and are pooled at a concentration of 2 µg/ml per peptide into two pools [12]. After an overnight incubation, IFN-gamma release will be detected using standard procedures. The average number of SFU counted in R10 wells will be subtracted from the average in individual HPV peptide wells and then adjusted to  $1 \times 10^6$  PBMCs for each HPV peptide pool. Additionally, PBMC responses against a pool of known antigenic epitopes combined from Cytomegalovirus, Epstein Barr Virus and Influenza (CEF) will be tested in order to track general cellular immune competence during the study in the same manner as HPV responses described above.
3. Evaluate cytotoxic T cells in response to HPV specific immunotherapy by flow cytometry. Additional assessment of cellular immune activity will occur via the application Flow Cytometry. Flow Cytometric assays will include an examination the influence of immunotherapy on the ability of patient T cells to exhibit phenotypic markers associated

with cytolytic potential after short-term stimulation by HPV E6 and E7 of VGX-3100 antigen (hereafter referred to as “CTL Phenotyping”), the ability of patient T cells to remain active in the presence of long-term antigen exposure and efficiently synthesize proteins used in lytic activity (hereafter referred to as “Lytic Granule Loading”) and the ability of patient T cells to effectively employ Granzyme B for the purposes of lytic degranulation and killing of target cells expressing HPV E6 and E7 (hereafter referred to as “Killing”). These panels may vary as newer information becomes available within the literature.

- i. The assay for CTL Phenotyping will employ a 6-hour *in vitro* stimulation of unfractionated patient PBMCs using peptides spanning VGX-3100 antigens as described above, an irrelevant peptide control (OVA) and a positive control (Staphylococcal Enterotoxin B or a combination of phorbol 12-myristate 13-acetate and Ionomycin). The CTL Phenotyping assay will examine the following external cellular markers: CD3, CD4, CD8 (T cell identification), CD45RO, CCR7 (memory subset identification), and CD107a. The CTL Phenotyping assay will additionally analyze the following intracellular markers: Interferon Gamma (Th1 biasing cytokine), Tumor Necrosis Factor Alpha, Granzyme A, Granzyme B and Perforin (proteins involved in lytic degranulation and cytotoxic potential). This panel of markers may vary as new information becomes available.
  - ii. The Lytic Granule Loading assay will employ a 120-hour *in vitro* stimulation of unfractionated patient PBMCs using peptides spanning VGX-3100 antigens, an irrelevant peptide control (OVA) and a positive control (Concanavalin A). The Lytic Granule Loading assay will examine the following external cellular markers: CD3, CD4, CD8 (T cell identification), and CD137 (also known as 41BB – marker of T cell activation). The Lytic Granule Loading assay will additionally analyze the following intracellular markers: Granzyme A, Granzyme B, Granulysin and Perforin (proteins involved in lytic degranulation and cytotoxic potential). This panel of markers may vary as new information becomes available.
  - iii. The Killing assay will employ a 120-hour *in vitro* stimulation of unfractionated patient PBMCs using peptides spanning VGX-3100 antigens. Stimulated whole PBMCs or CD8+ T cells isolated after the 120-hour incubation will be co-incubated for 60 minutes with target cells that have received a membrane stain that differentiates them from patient PBMCs/CD8+ T cells and have additionally been pulsed with a reagent which is activated only when the cell is actively in apoptosis (programmed cell death). At the end of this time cells will be washed and target cells identified using the membrane stain and analyzed for the presence of the active substrate as a measure of functional cytolytic degranulation and killing. Employment of this assay may change pending readouts from the Lytic Granule Loading assay. Description of previous use of these assays or variants thereof can be found in Bagarazzi *et al.* Immunotherapy against HPV16/18 [12]. The construction of this assay may vary as new information becomes available.
4. Evaluate tumor infiltrating lymphocytes (TIL) by Immunohistochemistry (IHC) on pre-surgical and surgical samples. HPV immunotherapy prior to surgery will provide us with a unique opportunity to determine if the VGX-3100 induced immune response can directly target the HPV positive tumor cells. Therefore, we will perform immunohistochemistry on

samples obtained prior to or at study entry as well as on samples that will be obtained from resection of the primary tumor in Cohort I.

### 3.2.3 Exploratory Endpoints: Clinical response criteria as determined by:

1. Any evidence of anti-tumor response as assessed by the Investigator
2. Progression free survival

## 4 Subject Selection and Withdrawal

Exceptions to eligibility will not be granted for this study.

### 4.1 Inclusion Criteria

1. Signed and dated written Ethics Committee approved informed consent.
2. Age  $\geq 18$  years.
3. Histologically confirmed HPV-positive mucosal squamous cell head and neck cancer. Tumor tissue samples and the HPV test results must be available prior to first dose of Study Treatment.
  - For pre-surgical subjects, p16 positivity must be confirmed prior to first dose
  - For subjects post chemoradiation therapy, HPV-16 and/or HPV-18 positivity (as assessed by p16 IHC AND oncogenic HPV ISH or PCR) must be confirmed prior to first dose.
4. Adequate bone marrow, hepatic, and renal function. ANC (Absolute Neutrophil Count)  $\geq 1.5 \times 10^9$  cell/ml, platelets  $\geq 75,000$  /mm^3, hemoglobin  $\geq 9.0$  g/dL, concentrations of total serum bilirubin within 1.5 x upper limit of normal (ULN), AST, ALT, CPK within 2.5 x ULN, and performed within 4 weeks prior to the first administration of Study Treatment.
5. ECG with no clinically significant findings as assessed by the investigator.
6. No history of clinically significant autoimmune disease, HIV infection or other immunosuppressive disease.
7. ECOG (Eastern Cooperative Oncology Group) performance status of 0-1.

8. Women of childbearing potential must have a negative serum pregnancy test and agree to remain sexually abstinent, have a partner who is sterile (i.e., vasectomy), or use two medically effective methods of contraception (e.g. oral contraception, barrier methods, spermicide, intrauterine device (IUD)). Males with reproductive potential must be willing to use a condom and have their female sexual partners use another form of contraception such as an IUD, spermicidal foam/gel/film/cream/suppository, diaphragm with spermicide, oral contraceptive, injectable progesterone, sub-dermal implant or a tubal ligation if the female partner could become pregnant. This requirement should be followed from screening through 24 weeks after last dose of immunotherapy.
9. Able and willing to comply with all study procedures.

## 4.2 Exclusion Criteria

1. Pregnant or breast-feeding subjects.
2. Anticipated concomitant immunosuppressive therapy (excluding non-systemic inhaled, topical skin and/or eye drop-containing corticosteroids).
3. Any concurrent condition requiring the continued use of systemic steroids (>10 mg prednisone or equivalent per day, see above) or the use of immunosuppressive agents. All other corticosteroids must be discontinued at least 4 weeks prior to first dose of study treatment.
4. Known history of hepatitis B or C with active viral replication.
5. Administration of any vaccine within 6 weeks of first dose of study treatment.
6. Tattoos, scars, or active lesions/rashes within 2 cm of the intended site of injection or if there is implanted metal within the same limb. Any device implanted in the chest (e.g., cardiac pacemaker or defibrillator) excludes the use of the deltoid muscle on the same side of the body.
7. Participation in another interventional clinical trial within 30 days before receiving first dose of study treatment. However, the subject may participate in an observational studies.
8. Any cardiac pre-excitation syndromes, e.g. Wolff-Parkinson-White syndrome.
9. Active drug or alcohol use or dependence that, in the opinion of the investigator, would interfere with adherence to study requirements
10. Prisoners or subjects who are compulsorily detained (involuntarily incarcerated) for treatment of either a psychiatric or physical (i.e. infectious disease) illness must not be enrolled into this study.
11. Any illness or condition that in the opinion of the investigator may affect the safety of the subject or the evaluation of any study endpoint.
12. Any other conditions judged by the investigator that would limit the evaluation of a subject.

## 4.3 Subject Recruitment and Screening

Subjects will be identified through the clinical practices of the co-investigators or sub-investigators in the Division of Medical Oncology, Division of Radiation Oncology and Division of Otolaryngology at the Hospital of the University of Pennsylvania and its affiliated hospitals and through referrals from outside hospitals and physicians. The trial will be publicized on the

website of the Abramson Cancer Center of the Hospital of the University of Pennsylvania. This protocol will also be listed in ClinicalTrials.gov database. Subjects will be required to give written consent of study participation before any screening tests or evaluations are conducted.

## **4.4 Early Withdrawal of Subjects**

### **4.4.1 When and How to Withdraw Subjects**

Subjects who do not complete the study protocol will be considered to have prematurely discontinued the study. The reasons for premature discontinuation (for example, voluntary withdrawal, toxicity, death) must be recorded on the case report form (CRF). Final study evaluations will be completed at the time of discontinuation if it is possible. Reasons for withdrawal include, but are not limited to the following:

1. Inter-current illness that would, in the judgment of the investigator, affect assessments of clinical status to a significant degree or require discontinuation of study;
2. Unacceptable toxicity: Subjects will be followed until resolution or stabilization;
3. Disease progression;
4. Subject withdraws consent;
5. Treatment delay greater than four weeks for any toxicity;
6. Subjects who do not have satisfactory compliance with study procedures;
7. Major protocol violations, including, but not limited to:
  - a. failure to meet major inclusion/exclusion criteria;
  - b. failure to complete full evaluations as required by protocol;
  - c. use of concomitant therapies.

If any subject in a cohort discontinues early for reasons other than toxicity from immunotherapy, consideration will be given for replacement.

If a subject discontinues Study Treatments before completion of long term follow up for 6 months post the last dose of immunotherapy, all assessments for the end of Study Treatment visit and/or end of study visit should be performed.

Subjects who have disease progression confirmed and/or start new anti-cancer therapy will be discontinued from the study. In both Cohorts, subjects who progress in their disease, once confirmed, will be required to come for the end of the study visit. All subjects will be followed for survival status regardless of the cause of death.

In the case of a fatal outcome, all relevant information (including cause of death, autopsy report, ER/hospital record, concomitant medication, and relationship to Study Treatment or underlying disease) will be collected.

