## 7 Statistical Plan

### 7.1 Sample Size Determination

A minimal of 20 but no more than 25 eligible subjects will be enrolled, as described above. This study is an estimation study, and as such, a power calculation is not applicable. Regarding the primary analysis, 20 subjects will provide 95% confidence that the true incidence of SAEs is <17% if 0 SAEs are observed. If more than one subject in a cohort discontinues early for reasons other than toxicity from the immunotherapy, consideration will be given for replacement.

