### 7.2 Statistical Methods

The primary analysis will estimate safety parameters. The incidence of SAEs and the incidence of injection site reactions will be estimated along with exact Clopper Pearson 95% confidence intervals. Toxicity experience will also be recorded and summarized.

In secondary analyses, immune response parameters will be estimated. For continuous outcomes, the mean and 95% confidence interval will be calculated using a t-distribution approach, and for binary outcomes, the proportion and exact Clopper Pearson 95% confidence interval will be calculated.

In exploratory analyses, we will also estimate the distributions of progression-free survival (PFS) and overall survival (OS) will be estimated, and any observed anti-tumor responses will be summarized. PFS and OS will be measured from the time of instillation of the initial dose of immunotherapy. Both The variables will be potentially censored by the end of the subject's observation. These distributions will be summarized using Kaplan-Meier survival curves and estimated median time to event of each type. Anti-tumor response category frequencies will be calculated.

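### Sections 4.4.1 and 7.1 give different triggers for replacing early leavers, and under section 7.3 an early progressor can be both left out of the main efficacy summaries and replaced

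*Combined protocol and SAP*

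**What the plan says.** The replacement rule appears twice, with different triggers.

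- Section 4.4.1: "If any subject in a cohort discontinues early for reasons other than toxicity from immunotherapy, consideration will be given for replacement".
- Section 7.1: "If more than one subject in a cohort discontinues early for reasons other than toxicity from the immunotherapy, consideration will be given for replacement".

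In both, toxicity from the immunotherapy is the only reason for leaving that falls outside the rule. Section 4.4.1 also lists disease progression among the reasons for withdrawal, gives death as an example of premature discontinuation, and adds: "Subjects who have disease progression confirmed and/or start new anti-cancer therapy will be discontinued from the study".

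On size, section 3.1 says of Cohort I: "A minimum of 5 eligible subjects will be enrolled to this cohort". Of Cohort II it says: "A minimum of 10 subjects will be enrolled into this cohort". Section 7.1 sets the total: "A minimal of 20 but no more than 25 eligible subjects will be enrolled, as described above".

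On analysis sets, section 7.3 keeps everyone with at least one dose in the safety analyses. It bases the main immunogenicity, survival and anti-tumor analyses on subjects who were given all the doses assigned to them. Section 7.2 measures PFS and OS from the first dose.

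**The concern.** There are two separate matters.

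First, an operating rule is written with two thresholds. Faced with a single early leaver in a cohort, the site finds one section that opens the question of replacement and another that does not. One loss is 1/5 = 20% of the Cohort I minimum, so the case is not trivial for that cohort.

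Second, the reasons for leaving that can lead to replacement include outcomes the trial reports. This matters because of section 7.3. Confirmed progression ends participation, so a subject who progresses before the last dose does not complete dosing and drops out of the main PFS, OS and anti-tumor analyses. Either replacement rule then allows a new subject to fill the place. The reported set looks complete, and the early failure is missing from it.

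**Working it through.** **1. The plan's own figure.** Section 7.1 states: "20 subjects will provide 95% confidence that the true incidence of SAEs is <17% if 0 SAEs are observed". Section 7.2 names exact Clopper-Pearson 95% intervals. With 0 events the upper limit is 1 − 0.025^(1/n).

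- n = 20: 1 − 0.025^(1/20) = 16.84%, which agrees with the stated bound.
- n = 19: 17.65%.
- n = 25: 13.72%.

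A leaver who was dosed stays in the safety set, so n does not fall. The statement would fail only if a subject who was never dosed left 19 treated and was not replaced.

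**2. Where the triggers differ.** Let k be the number of non-toxicity leavers in a cohort.

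| k | Section 4.4.1 | Section 7.1 |
|---|---|---|
| 0 | not triggered | not triggered |
| 1 | replacement considered | silent |
| 2 or more | replacement considered | replacement considered |

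The sections differ only at k = 1.

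**3. How often k = 1 would arise.** The documents give no discontinuation rate, so rates d of 5% to 30% are assumed, with subjects independent. P(k = 1) = n × d × (1 − d)^(n−1). For example, n = 5 and d = 0.10 gives 5 × 0.10 × 0.9^4 = 0.328.

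| Cohort size | d = 5% | d = 10% | d = 20% | d = 30% |
|---|---|---|---|---|
| 5 | 20% | 33% | 41% | 36% |
| 10 | 32% | 39% | 27% | 12% |
| 15 | 37% | 34% | 13% | 3% |

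The two cohort minima cannot both be the final sizes. With a total of at least 20, a Cohort I of 5 implies a Cohort II of at least 15, and a Cohort II of 10 implies a Cohort I of at least 10. The rows to pair are therefore 5 with 15, or 10 with 10. These figures show how often the wordings would diverge. They do not measure a change in any estimate.

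**4. Limit on size.** The minima sum to 5 + 10 = 15. Reaching 20 needs 5 further subjects in any case, and the cap allows 25 − 15 = 10. Relative to the minimum total, replacements can add at most 25 − 20 = 5.

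**5. Exclusion plus replacement.** Suppose five subjects are dosed and one progresses before the last dose. A replacement is enrolled, completes dosing and does not progress, as do the other four.

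- All dosed subjects: 1 progression in 6 (16.7%).
- Fully dosed subjects, as in the main analysis under 7.3: 0 in 5.
- Fully dosed subjects with no replacement: 0 in 4.

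The event is lost through the section 7.3 restriction. Replacement restores the apparent cohort size. The result is the same whichever trigger is used.

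**The case against.** The strongest reply is that little depends on the mismatch. Both sentences only offer consideration of replacement. A reader might infer that the sections give opposite instructions, or that 7.1 leaves Cohort I at four after one loss. The text does not support that: 7.1 is silent at one leaver and forbids nothing, the cohort figures are enrolment minima rather than completer targets, and at least five subjects beyond the minima must be enrolled anyway. This part of the reply stands.

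A reader might also infer that cohort make-up depends on which section is followed. It does not, since progression leavers are replaceable under both.

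Nor does replacement by itself delete anyone. Neither 4.4.1 nor 7.1 removes a replaced subject from analysis, and 4.4.1 and 4.4.2 follow all subjects for survival. That is correct, and it places the cause in 7.3. It does not remove the problem, because 7.3 read literally does exclude the early progressor from the main analysis.

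An outright bar on replacing subjects who progress or die is partly a design preference, and the documents do not compel it. Finally, PFS and anti-tumor response are exploratory in an estimation study without a power calculation. The Summary of Changes reports 19 subjects already followed beyond six months at this version, so at most 25 − 19 = 6 other enrolments fit under the cap. This lowers the stakes of the trigger. It does not settle how leavers and replacements are to be analyzed.

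**Conclusion.** The contradiction between 4.4.1 and 7.1 is real and must be reconciled. Its reach is narrow: exactly one non-toxicity leaver in a cohort, a discretionary rule, and a total held between 20 and 25. At assumed discontinuation rates of 5% to 30%, that case has a probability of 20% to 41% in a cohort of 5 and 3% to 37% in a cohort of 15.

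The more substantive matter holds under either wording. Restricting the main survival and anti-tumor analyses to fully dosed subjects, while allowing progression and non-treatment-death leavers to be replaced, biases those exploratory summaries favorably when someone progresses or dies before the last dose. The illustration of 0/5 against 1/6 shows the direction and a possible size in a small cohort. It is not a forecast, since the documents give no rate of early progression.

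A reader might infer that the primary safety analysis is compromised. It is not: the 16.84% bound reproduces, and dosed leavers remain in the safety set. The point is minor.

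**What to change.** - State one trigger, in the same words, in 4.4.1 and 7.1.
- State in 7.1 and 7.3 that any subject who received a dose, replaced or not, stays in the PFS, OS and anti-tumor denominators, as 7.3 already provides for safety.
- State that replacements are added only to complete the immune series, and count toward the cap of 25.
- Keep the fully dosed set as a supportive analysis for PFS, OS and anti-tumor response.

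The cost is wording in three sections. The downside is that the exploratory efficacy summaries will include partially treated subjects; the supportive full-dose analysis shows what difference that makes.

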**Post-Surgery (conti.):**

4. Subjects will receive up to 3 doses given 3 weeks ( $\pm$  3 days) apart. A total of 4 doses (pre- and post- surgery) will be administered.
5. Immunotherapy will be administered prior to adjuvant chemotherapy and/or radiation that may be indicated.
6. Adjuvant therapy will not be delayed due to immunotherapy.
7. Subjects will be followed for tumor status as per institutional standard of care.

**Cohort II:** Immunotherapy will start approximately 2-6 months after completion of definitive or adjuvant chemoradiation therapy in order to allow recovery from the treatment side effects of chemoradiation. INO-3112 will be delivered by IM injection followed by EP approximately once every 3 weeks for a total of 4 doses. A minimum of 10 eligible subjects will be enrolled into this cohort.

1. Subjects will be enrolled if they have HPV-16 and/or HPV-18 positive HNSCCa, and have completed chemoradiation therapy. Adequate tissue must be available to perform immunological correlates studies. Confirmation of HPV-16 and/or HPV-18 positivity is required prior to first dose of immunotherapy.
2. Subjects will be followed for tumor status as per normal institutional standard of care.

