## 3 Study Design

This will be a prospective, open-label, Phase I/IIa study of immunotherapy with INO-3112 in subjects with HPV-positive HNSCCa. Subjects will receive a course of treatment as described below and will be followed for safety as well as immune and clinical responses for 6 months from the last dose of immunotherapy.

The safety and effects of immunotherapy will be studied in two populations:

1. In chemo- and radiation-naïve subjects who undergo definitive surgery and
2. In subjects after chemoradiation therapy.

Doses of INO-3112 are based on safety experience in prior and on-going clinical trials. Based on the prior experience with these agents, dose escalation will not be conducted in this trial.

The study is divided into the following treatment cohorts:

- I. INO-3112 (6 mg VGX-3100 + 1 mg INO-9012) will be given to subjects before and after definitive surgery.
- II. INO-3112 (6mg VGX-3100 + 1 mg INO-9012) will be given to subjects after chemoradiation therapy.

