### **6.1.7 Long term follow up (every 3 months $\pm$ 7 days for 6 months)/End of study visit**

**Long term follow up for 6 months from the last dose of immunotherapy. End of study visit will be the last long term follow up visit.**

1. Medical/Clinical assessment including concomitant medications/treatments.
2. Complete physical examination including, but not limited to vital signs, weight and oxygen saturation.
3. ECOG Performance Status.
4. Review of adverse events.
5. Clinical laboratory testing including, but not limited to: CBC with differential and platelet count, total serum bilirubin, alkaline phosphatase, AST (SGOT), ALT (SGPT), serum creatinine, serum electrolytes, serum calcium and serum albumin.
6. Whole blood and serum for immunologic assays.

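### Section 4.4.1 does not exempt the adjuvant therapy anticipated for Cohort I from its discontinuation rule; read literally, it cuts short those subjects' 6-month follow-up

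*Combined protocol and SAP*

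**What the plan says.** - **Discontinuation (section 4.4.1).** "Subjects who have disease progression confirmed and/or start new anti-cancer therapy will be discontinued from the study." The object is the study, not only the study treatment. The same section lists "use of concomitant therapies", unqualified, as an example of a major protocol violation that can lead to withdrawal.
- **Cohort I pathway (section 3.1, Post-Surgery).** "Immunotherapy will be administered prior to adjuvant chemotherapy and/or radiation that may be indicated", and "Adjuvant therapy will not be delayed for immunotherapy." The synopsis has the same rule: "Adjuvant therapy will not be delayed due to immunotherapy."
- **Follow-up (section 3).** Subjects "will be followed for safety as well as immune and clinical responses for 6 months from the last dose of immunotherapy." Section 6.1.7 implements this for Cohort I with visits every three months. Each includes adverse-event review, laboratory tests and blood for immunologic assays.
- **What remains after discontinuation (sections 4.4.1 and 4.4.2).** Final evaluations are done if possible. End-of-treatment and/or end-of-study assessments are due when study treatment stops before the six-month follow-up is complete. Treatment-related toxicity is followed to resolution or stabilization, and survival status is collected for everyone.
- **Analysis (sections 7.2 and 7.3).** Every dosed subject is in the safety analyses. The main immunogenicity and survival analyses use subjects who received their assigned doses. PFS is censored at the end of observation, and nothing is said about adjuvant therapy.

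**The concern.** The protocol builds adjuvant therapy into the course of some Cohort I subjects, yet has a rule that appears to remove a subject from the study once such therapy starts. Subjects enter Cohort I naïve to chemotherapy and radiation, so either treatment begun after enrolment fits the ordinary meaning of new anti-cancer therapy. The rule joins progression and new therapy with and/or, so therapy without progression is enough to trigger it.

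If a site applies the rule as written, late observation is cut short in a subset defined by clinical indication. Three things are affected: late adverse events, which belong to the primary safety endpoint; duration of immune response in Cohort I (secondary objective 1c, section 2.2); and exploratory PFS. For PFS, censoring would fall at adjuvant start. Because that start depends on clinical indication, the censoring may be informative.

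**Working it through.** **1. The plan's own figure.** Section 7.1 says that 0 SAEs in 20 subjects gives 95% confidence that the true incidence is below 17%. The exact two-sided Clopper-Pearson upper limit with zero events is 1 − 0.025^(1/n). For n = 20 this is 1 − 0.025^(1/20) = 16.84%, so the figure reproduces. Section 7.3 keeps every dosed subject in the safety analyses, so n does not fall when follow-up is cut short, and the statement is unaffected.

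**2. When the rule would act.** Section 6.1.5 places the inspection visit at week 4 after surgery, and doses are three weeks apart. Assume that post-surgery dosing starts at that visit, and take 3 months as 13 weeks and 6 months as 26 weeks. With d post-surgery doses, the last dose is at week 4 + 3(d − 1).

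| Post-surgery doses | Last dose (week) | Month-3 visit (week) | Month-6 visit (week) |
|---|---|---|---|
| 1 | 4 | 17 | 30 |
| 2 | 7 | 20 | 33 |
| 3 | 10 | 23 | 36 |

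Adjuvant therapy that follows immunotherapy and is not held back for it would be expected to start during dosing or inside this follow-up window. The documents give no start time, so there are two cases:
- Start before month 3: both scheduled long-term visits are lost.
- Start between months 3 and 6: only the month-6 visit is lost.

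In either case an end-of-study assessment at discontinuation may supply one earlier, off-schedule set of the same data.

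**3. How many subjects.** The total is 20 to 25 (section 7.1), with at least 5 in Cohort I and at least 10 in Cohort II (section 3.1). Cohort I is therefore 5 to 20 − 10 = 10 subjects at the lower total, and 5 to 25 − 10 = 15 at the upper. The share who start adjuvant therapy is not stated, so the number affected can lie anywhere from none to all of Cohort I.

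**4. Illustration of the loss in late safety.** This is the zero-event upper limit among subjects with complete six-month follow-up only. The plan does not state this quantity.

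| Total | Cut short | Complete | Upper 95% limit |
|---|---|---|---|
| 20 | 0 | 20 | 16.8% |
| 20 | 3 | 17 | 19.5% |
| 20 | 5 | 15 | 21.8% |
| 20 | 10 | 10 | 30.8% |
| 25 | 0 | 25 | 13.7% |
| 25 | 5 | 20 | 16.8% |
| 25 | 10 | 15 | 21.8% |
| 25 | 15 | 10 | 30.8% |

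**5. Endpoint by endpoint.** Injection-site reactions are assessed 30 to 45 minutes after each dose, by diary for three days, and two weeks after the last dose (sections 6.1.2, 8.1.4 and 6.1.6). They are not listed at the long-term visits, so most of these data are safe; only an adjuvant start before the two-week visit would touch them. Adverse-event review, laboratory tests and immune samples are listed at the long-term visits and would stop. Section 8.1.8 places no duty on investigators to seek events actively beyond the follow-up period, although related events that they learn of must be reported.

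**The case against.** The strongest reply is that *new* may mean therapy outside the planned course. Section 4.4.1 pairs it with confirmed progression, its next sentence is about subjects who progress, and section 3.1 already foresees adjuvant therapy. That is a possible intention, and it means that forced removal of these subjects is a literal reading and not an established practice. But no section in the text states it, and the and/or wording points the other way. The public text breaks off in section 5.3.6 and resumes inside the screening list of section 6.1.1, so any lead-in to section 6.1 cannot be checked here.

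A second reply is that ending observation at new therapy can be deliberate, because it keeps chemotherapy and radiation effects out of the adverse-event and immune data. This stands as a real cost of continuing follow-up. It does not explain why sections 3 and 6.1.7 promise the full six months without qualification.

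Third, part of the immune and PFS loss has another source. If adjuvant therapy starts before dosing is complete, section 7.3 already leaves that subject out of the main immunogenicity and survival analyses. This stands for that subset only.

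A reader might also infer that the primary SAE estimate is compromised. It is not: the denominator and the <17% statement are unchanged, and follow-up of related toxicity and of survival continues.

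**Conclusion.** The conflict is real in the current text, and it should be removed by amendment. On the literal reading, a Cohort I subject who starts anticipated adjuvant therapy loses one or both scheduled long-term visits. A final assessment where possible, related-toxicity follow-up and survival status remain. The loss is of late adverse-event observation time, Cohort I data on immune response duration, and exploratory PFS follow-up with possibly informative censoring.

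This rests on two assumptions: that *new anti-cancer therapy* includes adjuvant therapy, and that adjuvant therapy starts within six months of the last dose.

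Three stronger inferences are tempting but unsupported:
- That every affected subject loses both visits. This needs a start before month 3, and it overlooks the end-of-study assessment.
- That a particular share of Cohort I is affected, or that at least one affected subject is nearly certain. The documents give no adjuvant rate.
- That the subjects who remain are a lower-risk group. Indication for adjuvant therapy makes selection plausible, but the documents do not describe the risk of either group.

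**What to change.** Reconcile the Cohort I post-surgery text (synopsis and section 3.1), the follow-up text (sections 3 and 6.1.7) and section 4.4.1:

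- In 4.4.1, separate discontinuation of study treatment from discontinuation of study follow-up. State that starting protocol-anticipated adjuvant therapy does not by itself end the scheduled adverse-event, laboratory and immune visits through six months.
- Clarify how the unqualified concomitant-therapy item in 4.4.1 applies to such therapy.
- Record the adjuvant start date on the CRF.
- In section 7.2, summarise safety and immune data before and after that date, and state how PFS handles it.

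Whether study dosing continues after adjuvant start is a clinical matter on which nothing is proposed here.

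The cost is amendment wording and one date field, since the visits are already in Table S1. The downside is that later adverse events and immune results will be mixed with adjuvant effects. The before/after summary makes this visible but cannot fully separate the two in a cohort of 5 to 15.
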